5.3 DEFINITION OF ANALYSIS SETS

The following definitions will be used for the efficacy and safety analysis sets.

All-treated population: All randomized or enrolled subjects who receive ≥1 dose of study drug.

Efficacy-evaluable population: All subjects in the All-treated population who have ≥1 response assessment after the first dose of study treatment.

The safety analyses and primary efficacy analyses for all efficacy endpoints will be performed on the All-treated population. Sensitivity analyses for efficacy will be carried out on the Efficacy-evaluable population.

5.4 MISSING DATA HANDLING

General Considerations: Subjects lost to follow-up (or who dropped out) will be included in statistical analyses up to the point of their last evaluation.

Duration of Response and Progression-Free Survival: Data for subjects without disease progression or death will be censored at the date of the last tumor assessment and before the initiation of alternative anticancer therapy. The details of the censoring rules will be provided in the Statistical Analysis Plan (SAP).

Time-to-Next Treatment: Data from subjects who have not received subsequent therapy will be censored at the earliest of death or the last time that lack of administration of a new therapy was objectively documented. The details of the censoring rules will be provided in the SAP.

Safety: Missing or partial start and end dates for AEs and concomitant medications will be imputed according to prespecified, conservative imputation rules. The details will be provided in the SAP. No other imputation of values for missing data will be performed.

5.5 ENDPOINT DATA ANALYSIS

5.5.1 Safety Endpoint

Safety summaries will include summaries in the form of tables and listings. The

frequency (number and percentage) of treatment emergent AEs will be reported in each treatment group by MedDRA System Organ Class and Preferred Term. Summaries will also be presented by the severity of the AE (per CTCAE, v4.03 for Part 1 and v5.0 for Parts 2 and 3) and by relationship to study drug.

Laboratory shift tables containing counts and percentages will be prepared by treatment assignment, laboratory parameter, and time. Summary tables will be prepared for each laboratory parameter. Figures of changes in laboratory parameters over time will be generated.

Results of vital sign assessments and physical exams will be tabulated and summarized.

5.5.2 Demographics and Baseline Characteristics

Additional analyses will include summaries of subject demographics, baseline characteristics, medical history, compliance, and prior and concurrent treatments. Concomitant medications will be coded according to the World Health Organization (WHO) Drug Dictionary and tabulated.

5.5.3 Study Treatment Administration and Compliance

Descriptive information will be provided regarding the number of acalabrutinib, lenalidomide, and rituximab doses prescribed, the total number of doses taken, the number of days of treatment, and the number and timing of prescribed dose reductions and interruptions.

For each subject, acalabrutinib and lenalidomide compliance will be described in terms of the proportion of study drug actually taken based on returned pill count relative to the amount that was dispensed (taking into account physician-prescribed modifications and interruptions).

5.5.4 Analysis of Efficacy Parameters

Overall Response Rate

ORR will be defined as the proportion of subjects who achieve a CR or PR according to the Lugano Classification for NHL (Cheson et al. 2014), as assessed by investigators. ORR will be calculated, and the corresponding 2-sided confidence interval will be derived.

Duration of Response

The DOR is defined as the interval from the first documentation of CR or PR to the earlier of the first documentation of definitive disease progression or death from any cause. Kaplan-Meier methods will be used to estimate event-free curves and

corresponding quantiles (including the median).

Progression-Free Survival

PFS is defined as the interval from the start of acalabrutinib therapy to the earlier of the first documentation of objective disease progression or death from any cause. Kaplan-Meier methods will be used to estimate the event-free curves and corresponding quantiles (including the median).

Time-to-Next Treatment

Time-to-next treatment defined as the time from start of acalabrutinib therapy on this protocol to the start of the next treatment. Kaplan-Meier methods will be used to estimate the event-free curves and corresponding quantiles (including the median). Data from subjects who have not received subsequent therapy will be censored at the earliest of death or the last time that lack of administration of a new therapy was objectively documented.

Time-to-next treatment data will be collected from subjects in Part 2 and Part 3 for an exploratory analysis.

Overall Survival

The duration of OS will be measured from the start of acalabrutinib therapy until the date of death. Subjects who are known to be alive as of their last known status will be censored at their date of last contact. Kaplan-Meier methodology will be used to estimate OS curves and corresponding quartiles (including the median).

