2.1.1 Primary Objective

 To characterize the safety profile of acalabrutinib alone or in combination with rituximab in subjects with R/R FL

2.1.2 Secondary Objectives:

- To characterize the safety profile of acalabrutinib in combination with rituximab in subjects with previously untreated FL
- To characterize the PK profile of acalabrutinib alone or in combination with rituximab
- To evaluate the PD effects of acalabrutinib alone or in combination with rituximab
- To evaluate the activity of acalabrutinib alone or in combination with rituximab as measured by ORR, DOR, time-to-next treatment, and PFS

2.2 PART 2

Please note that enrollment for Part 2, Cohort 2 (R/R MZL: Acalabrutinib + Rituximab) of this study is closed.

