3.2 END OF STUDY

The final data cut-off to support final database lock will be based on the projected median follow-up of approximately 30 months for subjects in Part 2 which is projected to occur approximately 23 months after last subject first dose, this is estimated to be approximately 25 August 2023. A median follow-up of approximately 30 months is deemed adequate follow-up for the FL and MZL population in this study. In addition to the above, a final data cut to support Part 1 final database lock will occur approximately 71 months after last subject first dose in Part 1; this is expected to provide adequate long-term follow up for the FL subjects enrolled in the study.

A Clinical Study Report (CSR) will be written using the final data cut-off for Part 1 and a second CSR will be written using the final data cut-off for Parts 2 and 3.

The end of the study is defined as the final data cut-off for the final analysis.

AstraZeneca will continue to supply acalabrutinib in the continued access phase of this study and after completion of this study while, in the opinion of the investigator, the subject is benefitting.

In the event that product development reaches a point where alternative product supply options become available, then these alternative product supply options will be discussed by the Sponsor with the investigator. The Sponsor will work with the investigator to transition the subject(s) to alternative supply, where possible.

It is recommended that investigators continue to observe ongoing subjects at the frequency employed prior to the primary DCO.

Protocol dose modification and stopping criteria are to be followed while a subject is receiving acalabrutinib. A change in the dose/schedule of acalabrutinib should only occur for safety reasons, based on the investigator's judgement, and should generally follow the approach for dose reduction and discontinuation as described in this protocol.

After the final DCO, the clinical database will close to new data, however SAEs must continue to be reported. Subjects may be withdrawn from the study at this time; however, they may remain on study treatment beyond closure of the database if, in the opinion of the Investigator, the subject continues to receive benefit from study treatment. Any subject who is eligible to continue receive acalabrutinib after database closure is considered to have completed the study when he/she meets one of the discontinuation

criteria listed in Section 3.8.

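### Time-to-next treatment (Part 1 secondary measure) censors untreated deaths in a Kaplan-Meier event-free curve, without stating the hypothetical estimand that this implies or planning a competing-risk estimate

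*Protocol*

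**What the plan says.** Protocol 5.5.4 defines time-to-next treatment as "the time from start of acalabrutinib therapy on this protocol to the start of the next treatment". Death is not part of the event. The section plans a Kaplan-Meier event-free curve with its quantiles, including the median, and states that subjects without a later therapy "will be censored at the earliest of death or the last time that lack of administration of a new therapy" was documented.

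Protocol 5.4, Missing Data Handling, gives the same rule: "Data from subjects who have not received subsequent therapy will be censored at the earliest of death" or the last documented absence of new therapy. It adds: "The details of the censoring rules will be provided in the SAP".

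In Protocol 2.1.2 the measure is part of a Part 1 secondary objective, activity "as measured by ORR, DOR, time-to-next treatment, and PFS". Protocol 3.2 sets the final Part 1 cut at "approximately 71 months after last subject first dose in Part 1", which is 71/12 = 5.9 years.

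By contrast, DOR and PFS in Protocol 5.5.4 also use the event-free label but count death from any cause as an event. The visible text plans neither a cumulative incidence of next treatment nor a composite of next treatment or death. The SAP supplied covers Parts 2 and 3 only, and the body of its section 7.6.5 on this endpoint is not visible.

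**The concern.** A subject who dies without a further therapy can never start one. Kaplan-Meier treats a censored subject as still at the same future risk as those who remain, so an untreated death is handled as if treatment were still to come. Two natural readings of the curve then go wrong. One minus the curve is higher than the proportion who actually start a next treatment. The curve itself is higher than the proportion alive without one, because subjects who died are not counted as leaving that state.

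The shared label makes the second misreading easy: for PFS the event-free proportion excludes the dead, and here it does not. Nearly six years of follow-up after the last first dose leaves time for untreated deaths to accumulate. Protocol 5.2 describes Part 1 as descriptive work to support further development, so the estimate and its interpretation are what Part 1 delivers for this endpoint.

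**Working it through.** **The plan's own figures.** It gives no number for time-to-next treatment. Its only Part 1 design figures are adverse-event detection probabilities. They reproduce as 1 − (1 − p)^n: 84.2% and 97.7% for n = 36, 46.0% and 71.8% for n = 12. They do not bear on this point.

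**Inputs.** From the protocol: the event, the censoring rule, the 71-month cut and 12 subjects per arm. Assumed, because the documents give neither: constant hazards, a 24-month median time to next treatment, and an untreated-death hazard equal to r times the treatment hazard.

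**Formulas at t = 60 months.** h1 = ln 2/24 = 0.02888 per month; h2 = r × h1.
- One minus Kaplan-Meier, deaths censored: 1 − exp(−h1 t) = 1 − exp(−1.733) = 82.3%. The curve stands at 17.7%.
- Actual probability of next treatment: h1/(h1 + h2) × [1 − exp(−(h1 + h2)t)].
- Alive without next treatment: exp(−(h1 + h2)t).
- Died untreated: the remainder.

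| r | Actual next treatment | Overstatement (points) | Alive without next treatment | Died untreated | Expected per 12 |
|---|---|---|---|---|---|
| 0 | 82.3% | 0 | 17.7% | 0% | 0 |
| 5% | 79.8% | 2.5 | 16.2% | 4.0% | 0.5 |
| 10% | 77.4% | 4.9 | 14.9% | 7.7% | 0.9 |
| 20% | 72.9% | 9.4 | 12.5% | 14.6% | 1.7 |
| 30% | 68.8% | 13.5 | 10.5% | 20.6% | 2.5 |

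Example, r = 10%: (1/1.1) × [1 − exp(−1.906)] = 0.8514/1.1 = 77.4%.

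**Second check, at the 71-month cut.** Here l = ln 2/median and mu = −ln(1 − d)/71, where d is the assumed risk of death by 71 months in the absence of next treatment. The 14-month row borrows the median PFS that Protocol 1.1 reports for ibrutinib in relapsed or refractory FL, as an illustration only.

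| Assumed median (months) | One minus KM | Actual, d = 5% | Actual, d = 30% | Overstatement (points) | Median with death as event (months) |
|---|---|---|---|---|---|
| 14 | 97.0% | 95.8% | 88.9% | 1.2 to 8.1 | 13.8 to 12.7 |
| 24 | 87.1% | 85.6% | 77.5% | 1.5 to 9.6 | 23.4 to 20.4 |
| 48 | 64.1% | 62.8% | 55.6% | 1.3 to 8.6 | 45.7 to 35.6 |

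Across these rows the curve exceeds the share alive without next treatment by 0.2 to 10.8 points; the largest gap is 35.9% against 25.1%.

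**Sampling error in one 12-subject arm.** With no untreated deaths, the SD of the 60-month figure is √(0.823 × 0.177/12) = 11.0 points, a 95% half-width of about 1.96 × 11.0 = 21.6 points. Simulation at 71 months, with 24- and 48-month medians and d of 10% to 30%, gives SDs of about 10 to 16 points. For a 24-month median the large-sample SD is 1/(2 × √12 × 0.5 × 0.02888) = 10.0 months.

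**The case against.** The strongest reply is that the event is defined as the start of next treatment alone. Kaplan-Meier with deaths censored is a legitimate estimate of time to that event if death is independent of treatment need, and the event-free label then follows from the definition. This stands. A reader might infer that the planned curve is wrong under any interpretation; the documents do not support that. What remains is that the protocol does not state the hypothetical estimand and plans no estimate for the two everyday readings.

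The second reply concerns weight, and most of it stands. No death rate is given, and Protocol 1.1 says most patients with indolent disease have had extended survival. The plan names the curve and quantiles, not a 60-month landmark. At r = 5% to 10%, the 24-month median would become 24/1.05 = 22.9 to 24/1.10 = 21.8 months with death as an event, a small shift beside an SD of about 10 months. Part 1 makes no formal comparison, and PFS and DOR already count deaths. However, a confidence interval reflects sampling error; it does not show a one-directional gap between the curve and the way it is read.

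Third, it may be doubted whether Part 1 records the deaths, since OS is not a Part 1 endpoint and Appendix 4 has no survival row. The existing rule already needs a death date, PFS counts deaths, Protocol 3.9 lists death as a study-exit reason, and Protocol 6.3.5 requires deaths due to progression to be entered in the data capture system. The data should be there.

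Finally, a reader might extend the point to Parts 2 and 3. Protocol 5.5.4 makes the analysis exploratory there, and the text of SAP 7.6.5 is not visible, so no defect can be claimed. No Part 1 SAP was supplied either; it may add such an analysis, though the protocol's rule is explicit.

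**Conclusion.** The concern holds for Part 1 as a modest, inexpensive improvement. Censoring untreated deaths makes one minus the curve overstate the actual probability of next treatment, and makes the curve overstate the share alive without it, unless the unstated hypothetical estimand is intended.

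The size cannot be fixed from the documents. The 60-month range rests on constant hazards, a 24-month median and an untreated-death hazard of 5% to 30% of the treatment hazard, all assumed. Other assumptions at 71 months give 1.2 to 9.6 points, and the gap vanishes if nobody dies untreated. A firm statement that the reported result will be materially biased would go beyond the documents. Nor do they require replacing the headline curve, which is a choice of definition.

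**What to change.** For Part 1, in Protocol 5.4 and 5.5.4 and the Part 1 analysis plan:
- Keep the planned Kaplan-Meier curve and median, and state in the text and on the output that deaths before next treatment are censored.
- Add the cumulative incidence of next treatment with death as a competing event (Aalen-Johansen).
- Report the number of deaths before next treatment by arm, so that readers can see whether the distinction matters.
- Use time to next treatment or death for any curve or median described as alive and free of next treatment.

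The cost is one extra analysis from data the existing rule already needs. The drawback is an additional figure that will not match reports that censor deaths; keeping the planned curve preserves that comparison. No change is proposed for Parts 2 and 3.

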5.5.5 Analysis of Pharmacokinetic/Pharmacodynamic Parameters

Part 1

The plasma pharmacokinetics of acalabrutinib in subjects receiving acalabrutinib alone or in combination with rituximab will be characterized using noncompartmental analysis. The following PK parameters will be calculated, whenever possible, from plasma concentrations of acalabrutinib:

- AUC_{0-t} Area under the plasma concentration-time curve calculated using linear trapezoidal summation from time 0 to time t, where t is the time of the last measurable concentration (C_t).
- AUC₀₋₁₂ Area under the plasma concentration-time curve from 0 to
 12 hours, calculated using linear trapezoidal summation.
- AUC_{0-∞} Area under the plasma concentration-time curve from 0 to infinity,

calculated using the formula: $AUC_{0-\infty} = AUC_{0-t} + C_t / \lambda_z$, where λ_z is the apparent terminal elimination rate constant.

- AUC_{0-24calc} Area under the plasma concentration-time curve from 0 to 24 hours, calculated by doubling the value for AUC₀₋₁₂.
- $\bullet \quad C_{\text{max}} \qquad \quad \text{Maximum observed plasma concentration}$
- T_{max} Time of the maximum plasma concentration (obtained without interpolation)
- t_{1/2} Terminal elimination half-life (whenever possible)
- λ_z Terminal elimination rate constant (whenever possible)
- CL/F Oral clearance
- Vz/F Oral volume of distribution

The PK parameters will be tabulated and summarized using descriptive statistics.

Part 2: There will be no PK analysis in Part 2.

Part 3

Plasma concentrations of acalabrutinib and ACP-5862 will be tabulated for each subject by arm, visit, and timepoint. Summary statistics (mean, median, standard deviation, percentage coefficient of variation) and plots will be presented, as appropriate.

Additional analyses, including population PK analysis, may be conducted as appropriate.

Part 1, Part 2, and Part 3

Missing dates or times may be imputed for PK and PD samples if the missing values can be established with an acceptable level of accuracy based on other information obtained during the visit in question. If PK and PD sampling for a given subject is not performed according to protocol instructions, that subject may be excluded from the PK and PD analyses.

For each PD variable, the concentration at each assessment will be described. The change from baseline to each assessment will be summarized. The best change from baseline during the study will also be summarized. As appropriate, the on-treatment values will be compared with the pretreatment baseline values using paired t-tests. P-values of ≤ 0.05 will be considered significant.

5.5.6 Explorative or Correlative Analyses

Additional PK or PD analyses may be performed, as deemed appropriate.

Correlations between subject characteristics and outcome measures and correlations among outcomes measures will be explored using regression models or other appropriate techniques.

6 ASSESSMENT OF SAFETY

Safety assessments will consist of monitoring and recording AEs and SAEs; measurements of protocol-specified hematology, clinical chemistry, urinalysis, and other laboratory variables; measurement of protocol-specified vital signs; and other protocol-specified tests that are deemed critical to the safety evaluation of the study drug(s).

6.1 REFERENCE SAFETY INFORMATION

For the purpose of reporting AEs and SAEs:

 The Investigator Brochure contains the Reference Safety Information (RSI) for acalabrutinib

6.2 **DEFINITIONS**

6.2.1 Adverse Events

An AE is any unfavorable and unintended sign, symptom, or disease temporally associated with the use of an investigational (medicinal) product, regardless of attribution of causality.

This includes the following:

- AEs not previously observed in the subject that emerge during the protocol-specified AE reporting period, including signs or symptoms associated with NHL that were not present before the AE reporting period (see Section 6.3.1).
- Pre-existing medical conditions (other than the condition being studied) judged by the investigator to have worsened in severity or frequency or changed in character during the protocol-specified AE reporting period.

Abnormal laboratory values considered clinically significant by the investigator should be reported as an AE. For actions required for liver toxicity, refer to Appendix 7.

The following are NOT considered an AE:

Pre-existing condition that has not worsened: A pre-existing condition
 (documented on the medical history eCRF) is not considered an AE unless the

severity, frequency, or character of the event worsens during the reporting period.

- Preplanned hospitalization: A hospitalization planned before signing the ICF is not considered an SAE but rather a therapeutic intervention. However, if during the preplanned hospitalization an event occurs, which prolongs the hospitalization or meets any other SAE criteria, the event will be considered an SAE. Surgeries or interventions that were under consideration, but not performed before signing the ICF, will not be considered serious if they are performed after signing the ICF for a condition that has not changed from its baseline level. Elective hospitalizations for social reasons, solely for the administration of chemotherapy, or due to long travel distances are also not considered SAEs.
- Diagnostic testing and procedures: Testing and procedures should not be reported as AEs or SAEs, but rather the cause for the test or procedure should be reported. If a test or procedure is performed to rule out a diagnosis, the sign or symptom leading to the test/procedure should be the event term, and the event term should only be updated to the diagnosis if/when a diagnosis is confirmed. Testing and procedures performed solely as screening measures (e.g., routine screening mammography or colonoscopy) should not be reported as AEs or SAEs.
- Abnormal laboratory results the investigator considers to not be clinically significant: Abnormal laboratory results are not AEs unless they are clinically significant. For example, a clinically significant laboratory result is one that requires treatment (for example a blood transfusion for low hemoglobin) or requires a change in study drug (e.g., lowering the dose or withholding study drug while the laboratory finding resolves or stabilizes).
- Progression of underlying malignancy: Progression of underlying malignancy will not be reported as an AE if it is clearly consistent with the suspected progression of the underlying cancer. Hospitalization due solely to the progression of underlying malignancy should NOT be reported as an SAE. Clinical symptoms of progression may be reported as AEs if the symptoms cannot be determined as exclusively due to the progression of the underlying malignancy, or if they do not fit the expected pattern of progression for the disease under study.
- If there is any uncertainty about an AE being due only to the disease under study, it should be reported as an AE or SAE.

